15.2 Field trial eligibility criteria

1. Participant lives in the designated study site
2. Participating households must be within a one-hour drive of Feya General Hospital
3. Participant considers themselves to be in good health, as does the parent or guardian
4. Participant is aged 3 years and ≤ 12 years
5. Participant has a good understanding of the procedures of the study and agrees to abide to these procedures
6. The parent or guardian of the participant has a good understanding of the procedures of the study and agrees to abide to these procedures
7. Participant is able to communicate well with the investigator or fieldworker who is conducting the study
8. Participant has no known adverse reactions to the commercially available repellents DEET, PMD, IR3535, Picaridin or Permethrin, or to Vanilla
9. Participant has no known history of skin allergies or hypersensitivity to topical creams
10. Participant agrees to a pre-trial skin reactivity test for all the repellents that will be used in the trial
11. If in the event of the participant experiencing an adverse reaction to a repellent during the trial, the participant can request medical advice from the Stronger-SAFE field team nurses if they wish
12. Participant is willing to sit still on a chair outside their house, for sequential periods of up to ten minutes, allowing wild fly contact and landing on the body and face, as much as possible without disturbing fly behaviour
13. Participant agrees not to use any perfumed or scented product, including bathing products, for a 24-hour period before each laboratory session

14. Able and willing to give fully informed assent
15. The parent or guardian has signed informed consent
16. The participant does not become unacceptably upset during the procedures

15.3 Participant withdrawal

Participants can stop at any time without giving a reason for withdrawing. Data collected to the point of withdrawal will be used in the analysis of the study, unless the participant requests that their data is not used, in which case it will be removed from the database. Participants may also be removed at the discretion of the Chief Investigator, where continued participation may affect the safety of the participant or where there is a development of any condition which might interfere with study participation.

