26.1 Data collection

26.1.1 Laboratory trials

Data to be collected are: Participant name and ID number, address, phone number and email address, confirmation of informed consent, date of birth, eligibility details, topical repellent skin test details (active ingredient, amount, 24 h assessment), visit details (date and time of visit to

testing facility, investigator conducting testing, person variables [body weight, tympanic temperature], temperature and humidity of testing room, repellent product and concentration tested, testing variables [Number of *Musca sorbens* flies, number of different sex, age of flies, video file ID] and adverse event monitoring).

All arm-in-cage observation and videoing will be conducted by the laboratory co-PI or GCP trained staff, as will application of the repellent product. All investigators involved in the trial will be trained in the study requirements and will follow standard operating procedures, to ensure each participant is studied in a uniform and reproducible manner.

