26.1.2 Field trials

Data to be collected are: Participant, household and kebele name and ID number, phone number, woreda name, confirmation of informed consent, date of birth, eligibility details, topical repellent skin test details (active ingredient, amount, 24 h assessment), visit details (date and time of visit, fieldworkers conducting testing, person variables [ocular or nasal secretions, body weight, tympanic temperature], environmental conditions, repellent product and concentration tested, number of fly-eye, -nose, -mouth and -face contacts, video recording of face), adverse event monitoring and qualitative data from the end-of-trial product acceptability interviews.

All fly-eye observation and videoing will be conducted by trained entomological fieldworkers with experience in fly-eye studies. Application of the repellents will be conducted by qualified ophthalmic nurses. All fieldworkers involved in the trial will be trained in the study requirements and will follow standard operating procedures, to ensure each participant is studied in a uniform and reproducible manner.

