28.1 Adverse events

Participants will be monitored throughout testing sessions by investigational staff (fieldworkers in the field clinical trials) for any adverse events. If any adverse events related to the repellent product are apparent at any time during the trial, testing will stop immediately. In laboratory trials, details of how to access treatment will be offered, and in field trials the participant will be assessed by the ophthalmic nurse in the field team.

Volunteers can only participate in a test a minimum of 72 hours after the screening for skin sensitivity to the repellent product, and participants with known allergies to any of the product ingredients will not be eligible to take part. Within 72 hours after testing, the participant will be contacted and asked to report any adverse events that might have occurred since the end of testing. Adverse events that occur >72 hours after the end of participation in the trial will be passively monitored.

An adverse event which is ongoing at the time of participant withdrawal or completion will be followed up until it resolves or until 30 days after the participant terminates from the study, whichever comes first.

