28.3 Reporting Procedures

All adverse events and serious adverse events will be reported to the appropriate regulatory authorities. Depending on the nature of the event the reporting procedures detailed below should be followed. Any questions concerning adverse event reporting should be directed to the CI in the first instance. For adverse event reporting, all data will be recorded via electronic data capture using ODK, then managed and stored as per section 26.

For all participants in both laboratory and field trials, the correct course of action for reporting adverse events is given in Appendix 18. Safety Reporting Flowchart_All. Any AEs occurring in participants in the Field Trial be reported in accordance with the expectations of specific regulatory bodies in Ethiopia, for which the correct course of action for reporting is given in Appendix 19. Safety Reporting Flowchart_Ethiopia.

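### Section 15.3 orders removal of a withdrawing participant's data from the database on request, with no exception for the adverse event data that section 28 requires to be recorded, reported and followed

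*Combined protocol and SAP*

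**What the plan says.** Section 15.3 sets a default and an exception. The default is: "Data collected to the point of withdrawal will be used in the analysis of the study". The exception is: "unless the participant requests that their data is not used, in which case it will be removed from the database". No data type is named in either part.

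Section 26.1 counts safety information as collected data. For the laboratory trials the list ends with "age of flies, video file ID] and adverse event monitoring". For the field trials it ends with "adverse event monitoring and qualitative data from the end-of-trial product acceptability interviews".

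Section 28.3 says where that information sits: "For adverse event reporting, all data will be recorded via electronic data capture using ODK, then managed and stored as per section 26". It also sets the reporting duty: "All adverse events and serious adverse events will be reported to the appropriate regulatory authorities". Section 28.1 extends follow-up past withdrawal: "An adverse event which is ongoing at the time of participant withdrawal or completion will be followed up until it resolves", or for 30 days after the participant leaves the study if that is sooner. Section 28.3.1 requires every non-serious event to be logged. Section 28.3.2 requires every SAE to be recorded, with a report to the chief investigator in 24 hours and, for field events, to the Ethiopian authorities in 48 hours. None of these duties is lifted for someone who has withdrawn.

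Section 26.2 keeps study documentation for at least 10 years. Sections 26.2.1 and 26.2.2 hold adverse event questionnaires and records on paper, with scanned back-ups.

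**The concern.** A data manager who receives a removal request from the family of a child who has had a skin or eye reaction has two instructions. Section 15.3 says to take the data out of the database. Section 28 says to record the event there, report it and go on following it. The protocol gives no order of precedence.

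What is at stake is how complete the electronic safety data are. Under section 26.2 the final dataset is archived and anonymised versions are made public. Under section 29.5 the steering committee and the DMC have access to the project datasets, and section 27.1 gives the DMC the safety data to monitor. An event removed from the database would be missing from whatever is drawn from it afterwards. In the field trial the topical products go on the faces of children aged three to 12, and section 22.2 itself describes eye irritation with each of the three topical actives.

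The loss would also be selective if families of affected children ask for removal more often than others. That is plausible, but the documents say nothing about it.

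**Working it through.** **The two rules side by side**

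1. *Does the removal rule reach adverse event data?* Section 15.3 covers the participant's data without qualification, and sections 26.1.1 and 26.1.2 list adverse event monitoring as data to be collected. On the literal wording, yes.
2. *Are those data in the database?* Section 28.3 sends them to ODK and then to section 26, which uploads ODK data to the secure server. Yes.
3. *Does section 28 release withdrawn participants from its duties?* No. Section 28.1 expressly includes them.
4. *Does any section reconcile the two?* None was found in 15.3, 26.2, 28 or 29.3. The consent and assent forms (Appendices 3 and 7) were not available for this check.
5. *What survives a removal?* The paper records and scanned back-ups, and reports already sent. An SAE in the field is due to the authorities in 48 hours, so it will usually be reported first. A non-serious event is more exposed: the Ethiopian summary is issued every three months or at the end of the trial if sooner (28.3.1), and Table 5 schedules the field trial over three months. A removal could therefore come before the first summary.

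**The group sizes the illustration uses**

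- Field (19.2): difference 30%, SD 30%, power 90%. Alpha is not stated; with two-sided 0.05 assumed, the t-test calculation gives 22.02, rounded up to 23. Then 23 × 1.25 = 28.75, rounded up to 29. The plan's figures reproduce.
- Laboratory (19.1): (1.96 × 30/15)² = 15.4, rounded up to 16, and 17 after the 5% allowance. These reproduce too.

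**What one removal does to a count taken from the database**

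The event and removal counts are assumptions. Exact (Clopper-Pearson) 95% limits are used; for 0/n the upper limit is 1 − 0.025^(1/n).

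| Assumed case | All kept | After removal |
|---|---|---|
| Field arm, 1 reaction, that child removed | 1/29 = 3.4% (0.1 to 17.8) | 0/28 = 0% (upper limit 1 − 0.025^(1/28) = 12.3%) |
| Field arm, 2 reactions, both removed | 2/29 = 6.9% (0.9 to 22.8) | 0/27 = 0% (upper limit 12.8%) |
| Laboratory, 1 reaction, that adult removed | 1/17 = 5.9% (0.2 to 28.7) | 0/16 = 0% (upper limit 20.6%) |
| Field arm, 1 reaction, an unaffected child removed | 1/29 = 3.4% | 1/28 = 3.6% |

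The last row shows that the effect depends on who asks. Removing an unaffected child barely moves the figure.

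**Chance that at least one reaction shows in the database, field arm of 29**

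With reaction rate p and a share q of affected children removed, the chance is 1 − (1 − p(1 − q))^29.

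| p | q = 0 | q = 25% | q = 50% |
|---|---|---|---|
| 2% | 44.3% | 35.5% | 25.3% |
| 5% | 77.4% | 67.0% | 52.0% |
| 10% | 95.3% | 89.6% | 77.4% |

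The documents give neither p nor q, so these figures show a range and predict nothing.

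**The case against.** The strongest reply is that section 15.3 is a sentence about use in the analysis, not about safety records. It does not say that every kind of data goes, and it does not mention adverse events. Section 28.1 deals specifically with events open at withdrawal, and a specific safety rule would ordinarily prevail over a general one. Removal needs a request, and ordinary withdrawal keeps the data. ODK has an audit trail, and section 26.2 sets a retention period. How far a participant's right to removal extends is also a matter for the ethics committees, since section 29.3 ties consent to GDPR and wants it easy to withdraw.

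Much of this stands, and it limits the point. It does not supply the missing rule. The second half of the sentence in 15.3 goes beyond analysis: it directs removal from the database. The precedence of section 28 has to be assumed, because the protocol does not state it.

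Three stronger conclusions might be inferred, and the documents do not support them:

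- *That reactions would disappear from the trial.* Section 15.3 reaches the database only. Sections 26.2.1, 26.2.2 and 28.3.2 leave paper records, scanned back-ups and reports already made.
- *That the child drops out of the randomised count.* Section 15.3 does not mention allocation, enrolment or withdrawal counts, and consent and screening forms are also held on paper.
- *That a distorted tolerability rate would drive the Phase 3 choice.* Sections 17 and 26.3 plan no adverse event rate per arm, and section 16.2.2 names Protective Efficacy and the other outcome measures as the inputs. The DMC's named interim looks are after the laboratory stages.

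**Conclusion.** The point holds as a conflict between two stated rules. Applied literally after a reaction, section 15.3 would take an adverse event out of the electronic database, and out of later summaries and the archived dataset, while sections 26.2 and 28 require it to be recorded, reported, followed and retained.

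Severity is minor. In a field arm of 29, one removal can turn 3.4% into an apparent zero, but that rests on an assumed single reaction whose family asks for removal. The reaction rate and the frequency of requests are both unknown. The effect is on descriptive safety data only: no sample size, power, endpoint or efficacy estimate changes. The consent and assent forms may already say that safety data are kept, in which case section 15.3 only has to be brought into line with them.

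**What to change.** Amend section 15.3 so that a removal request takes out the participant's video and fly-contact outcome data, while adverse event and SAE records, the allocated arm, and the fact and date of withdrawal are kept under the study ID. Add a cross-reference to sections 26.2 and 28 so that the order of precedence is explicit. Check that the consent and assent forms say the same, and add it if they do not. In the trial report, give for each arm the number withdrawn and the number whose outcome data were removed.

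The cost is protocol wording and possibly consent wording, best settled before enrolment. The downside is that participants could withdraw their outcome data but not their safety record. The ethics committees would have to accept that, and families would have to be told in advance.

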15.4 Participant retention

Once participants are enrolled to either the laboratory or field clinical trial, both study sites will make every reasonable attempt to ensure that these participants are followed for the entire study period, when repeat observations are necessary over a duration of one month for the wearable repellent devices.

For the laboratory clinical trial, the loss-to-follow-up over this month is expected to be low, and 5 % loss-to-follow-up has been allowed for the laboratory trial sample size (+ one child). For the field clinical trial, loss-to-follow-up over that month is expected to be higher, as it may be harder to locate young children and ensure that they are at home on the required days. Therefore, a 25 % loss-to-follow-up has been allowed for the field trial sample size (+ six children). Fieldworkers at this study site will be responsible for developing and implementing local standard operating procedures to achieve this level of follow-up.

16 Interventions

16.1 Investigational products

16.1.1 Topical insect repellent products

One or more of three insect repellent products (Table 1), previously determined by laboratory experiments at LSHTM to exhibit potential repellency to *Musca sorbens*, will be tested.

Table 1. Insect repellent products that will be applied topically will be selected from these three actives

Generic name	Repellent active ingredient	CAS number	Manufacturer
DEET	N,N-Diethyl-meta-toluamide	134-62-3	Merck ⁽¹⁾
IR3535	3-[N-butyl-N-acetyl]-aminopropionic acid ethyl ester	52304-36-6	Merck ⁽²⁾
Picaridin	2-(2-hydroxyethyl)-1-piperidinecarboxylic acid 1-methylpropyl ester	119515-38-7	Alfa chemistry ⁽³⁾

⁽¹⁾ <https://www.sigmaaldrich.com/catalog/substance/deet1912713462311?lang=en®ion=GB>

⁽²⁾ https://origin-webqws.sial.com/catalog/product/sial/34524?lang=en®ion=GB&cm_sp=Insite--recent_fixed--recent5-3

⁽³⁾ <https://www.alfa-chemistry.com/sec-butyl-2-2-hydroxyethyl-piperidine-1-carboxylate-cas-119515-38-7-item-289774.htm>

16.1.2 Wearable repellent devices

One or more of five insect repellent products, with the possible addition of vanillin (Table 2), previously determined by laboratory experiments at LSHTM to exhibit potential repellency to *Musca sorbens*, and formulated into long-lasting plastic formulations made of low-density polyethylene (LDPE) or high-density polyethylene (HDPE). In the case of permethrin, the wearable repellent technology will be permethrin-treated fabric, e.g. a permethrin treated neckband. PMD will be allowed in a wearable repellent device, but not as a topical product, because of safety advice against its use on children's faces (57). Vanillin is an organic compound that it is thought may enhance the protection time of insect repellents.

Table 2. Insect repellent products that will be formulated into long-lasting plastic formulations will be selected from these five actives

Generic name	Repellent active ingredient*	CAS number	Manufacturer
DEET	N,N -Diethyl-meta-toluamide	134-62-3	Merck ⁽¹⁾
Oil of Lemon Eucalyptus, PMD	para-Mentane-3,8-diol OR Citriodiol® (64% PMD [a mixture of the cis and trans isomers of p-mentane-3,8-diol) together with a number of minor constituents found in essential oil which enhance the efficacy further])	42822-86-6	Merck ⁽²⁾ Citrefine ⁽³⁾
IR3535	3-[N-butyl-N-acetyl]-aminopropionic acid ethyl ester	52304-36-6	Merck ⁽⁴⁾
Picaridin	2-(2-hydroxyethyl)-1-piperidinecarboxylic acid 1-methylpropyl ester	119515-38-7	Alfa chemistry ⁽⁵⁾
Permethrin	(m-Phenoxybenzyl)-cis,trans-3-(2,2-dichlorovinyl)-2,2-dimethylcyclopropanecarboxylate	52645-53-1	Merck ⁽⁶⁾ OR Fagron Hellas ⁽⁷⁾

*Vanillin (4-Hydroxy-3-methoxybenzaldehyde, CAS number 121-33-5, available from Merck) may be used as a synergist with these repellent actives (<https://origin-webqws.sial.com/catalog/product/sial/v1104?lang=en®ion=GB>)

⁽¹⁾ <https://www.sigmaaldrich.com/catalog/substance/deet1912713462311?lang=en®ion=GB>

⁽²⁾ <https://origin-webqws.sial.com/catalog/product/aldrich/r751898?lang=en®ion=GB>

⁽³⁾ <https://www.citrefine.com/citriodiol/#what-is-citriodiol>

⁽⁴⁾ https://origin-webqws.sial.com/catalog/product/sial/34524?lang=en®ion=GB&cm_sp=Insite--recent_fixed--recent5-3

⁽⁵⁾ <https://www.alfa-chemistry.com/sec-butyl-2-2-hydroxyethyl-piperidine-1-carboxylate-cas-119515-38-7-item-289774.htm>

⁽⁶⁾ <https://origin-webqws.sial.com/catalog/product/sial/45614?lang=en®ion=GB>

⁽⁷⁾ <https://gr.fagron.com/en-gr>

16.2 Application of topical products

All topical products will be applied at the standard laboratory application rate of 1 ml product/600 cm².

16.2.1 Laboratory trials application rate

The arm is an estimated 9 % of the adult body surface area (BSA), therefore the forearm and hand can be considered to be 4.5 %. With the average adult BSA of 19,000 cm², the surface area of the forearm can be taken to be 855 cm². As such, 1.4 ml of solution will be applied to the forearm at the appropriate concentration, never exceeding 20 %.

16.2.2 Field trials application rate

Topical repellent will be applied to a circular area on the cheek. An average diameter of 6 cm would give a surface area of 28.3 cm². As such, 0.05 ml (50 µL) of product will be applied to each cheek at the appropriate concentration, never exceeding 20 %. Topical repellents will be applied at least 3 cm (three finger-breadths) below the eye and positioned away from the nose and mouth.

Due to the differences in surface area under observation in the laboratory and field trials, with greater skin surface areas in the former (application on the arm) leading to greater amounts of active ingredient being applied, there is a risk that efficacy in the laboratory will be greater than that experienced in the field. However, it should be emphasised that the aim of the laboratory trials is to inform which repellents can be taken into the field trial for testing, as this is the context in which such a product would be used. Therefore, while both studies are merited, the Protective Efficacy and other outcome measures as calculated in the field trial will be those that are used to inform inclusion of repellents as a fly-control intervention in the Stronger-SAFE Phase 3 RCT.

17 Study outcomes

17.1 Primary outcome measures

[figure not shown]
The primary endpoint is the protective efficacy of the repellent products. Protective efficacy will be presented as a proportion, by comparing fly contact on the participants following application of the repellent product (test), relative to before application (control) (see section 26.3). Protective efficacy will be determined for all repellent products in both the laboratory and field clinical trials.

17.2 Secondary outcome measures

1. Median Complete Protection Time (mCPT) in laboratory trials only
2. Median Effective Dose (ED₅₀), in laboratory trials only
3. Median Effective Time (ET₅₀), in both laboratory and field trials
4. Acceptability of the repellent interventions among children and their caregivers, in field trials only

18 Participant timeline

A timeline of participant recruitment and enrolment, consent, and completion of the clinical trials is given in Figure 4.

Figure 4. Participant timeline for clinical trials of insect repellents against fly contact by *Musca sorbens*

19 Sample size

19.1 Laboratory trials sample size

For laboratory trials, estimations of the sample size required are dependent on the variability of PE between individuals. As such, a range of sample sizes were calculated that took both this, and variability in the confidence intervals around the estimate, into consideration (Table 3). A conservative estimate of the PE standard deviation of 30 % was chosen, which when allowing for a confidence interval of ± 15 % around the estimate, gives a sample of 16 people. When allowing for 5 % loss-to-follow-up, the total sample size will be 17 people. Equal numbers of male and female participants are preferred.

Table 3. Estimation of sample size for determining the Protective Efficacy of repellent products in laboratory trials.

		Standard deviation of Protective Efficacy					
		10 %	15 %	20 %	25 %	30 %	35 %
Margin of error (CI)	5 %	16	35	62	97	139	189
	10 %	4	9	16	25	35	48

	15 %	2	4	7	11	16	21
	20 %	1	3	4	7	9	12

For stage two laboratory trials (repellent product persistence), multiple follow-ups on the same individuals will generate more repeat data points. As such, the sample size requirement for PE will be sufficient. If we observe in stage one that variability between individuals was much greater than expected then we will consider increasing the sample size for stage two.

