26.3 Data analysis

26.3.1 Protective Efficacy, p

The protection (protective efficacy, p) afforded by a repellent product will be presented as a percentage. p will be estimated by comparing fly-arm contact duration and fly-eye contact frequency, in laboratory and field trials respectively, after application (or wearing) of the repellent product to that during the control period.

Equation 1. Protective Efficacy, p

$$p = 100 \times ((C - T)/C)$$

Where (laboratory trials):

- C is the total duration of fly-arm contact before application of repellent ('control' measure), and
- T is the total duration of fly-arm contact after application of repellent ('treatment' measure)

Where (field trials):

- C is the frequency of fly-eye contacts before application of repellent ('control' measure), and

- T is the frequency of fly-eye contacts after application of repellent ('treatment' measure)

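### The ±15 % precision behind the laboratory sample size treats the SD as known; with an estimated SD of 30 %, 16 completers give about ±16 % and 17 give ±15.4 % (minor)

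*Combined protocol and SAP*

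**What the plan says.** Section 19.1 sizes the laboratory trial on the precision of the PE estimate. On the SD it says: "A conservative estimate of the PE standard deviation of 30 % was chosen". It continues that this SD, "when allowing for a confidence interval of ± 15 % around the estimate, gives a sample of 16 people", and then: "When allowing for 5 % loss-to-follow-up, the total sample size will be 17 people". Table 3 gives the number of people for SDs of 10 to 35 % and margins of ±5 to ±20 %.

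No confidence level, quantile or interval method is named there. Section 26.3.1 defines PE as 100 × (C − T)/C and says how it will be reported ("The protection (protective efficacy, p) afforded by a repellent product will be presented as a percentage"), but gives no confidence interval. Section 19.1 adds that a larger stage-two sample will be considered if stage one shows much more variability between individuals than expected. The SD is therefore a planning value that the trial itself will estimate.

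**The concern.** The precision figure is the only justification given for the laboratory sample size, and PE is the primary endpoint. A margin based on 1.96 is right when the SD is known. With about 16 people and an SD taken from the same data, a 95 % interval needs the t quantile, which is noticeably larger at that size. The stated ±15 % is then slightly optimistic for the design as planned.

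Table 3 itself shows the limit of the approximation: for SD 10 % and ±20 % it gives one person, from whom no SD, and so no interval, can be obtained. The table also matters later. A team that finds a larger SD in stage one and returns to Table 3 to resize stage two would read numbers that are two or three people too low.

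**Working it through.** **Inputs.** From section 19.1: SD 30 %, margin ±15 %, n = 16, 5 % loss, 17 enrolled. Assumptions, because the documents do not state them: a two-sided 95 % interval, a t interval at analysis, and roughly normal PE values.

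**1. Reproduce the plan's figure.** n = ceil((z × SD / margin)²). With z = 1.96: (1.96 × 30/15)² = 15.37, rounded up to 16. For losses, 16/0.95 = 16.84, rounded up to 17. The same formula reproduces all 24 cells of Table 3.

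The table also fixes the multiplier. The entry 25 (SD 25 %, ±10 %) requires (2.5z)² > 24, so z > 1.9596. The entry 189 (SD 35 %, ±5 %) requires (7z)² ≤ 189, so z ≤ 1.964. Hence the inference of a two-sided 95 % normal quantile.

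**2. Half-width when the observed SD is 30 %.** Half-width = t(0.975, n − 1) × 30/√n.

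| Completers | Normal quantile | t quantile | t half-width |
|---|---|---|---|
| 16 | ±14.70 % | 2.131 | ±15.99 % |
| 17 | ±14.26 % | 2.120 | ±15.42 % |
| 18 | ±13.86 % | 2.110 | ±14.92 % |

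The smallest n that meets ±15 % is 18 completers, or 19 enrolled (18/0.95 = 18.95).

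**3. Expected half-width when the true SD is 30 %.** The sample SD is on average a little below the true SD, so the average half-width is slightly smaller than in step 2: 15.72 % at n = 16, 15.19 % at n = 17 and 14.70 % at n = 18. The chance that the realised half-width is 15 % or less is 41 %, 48 % and 56 % respectively.

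**4. SD at which ±15 % is met.** SD = 15 × √n / t. For n = 16: 15 × 4/2.131 = 28.1 %. For n = 17: 15 × 4.123/2.120 = 29.2 %.

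**5. Keeping 1.96 at analysis.** With an estimated SD and n = 16, a nominal 95 % interval built with 1.96 covers about 93.1 %.

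**6. Table 3 with the t distribution** (current entry → t-based entry):

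| Margin | SD 10 % | 15 % | 20 % | 25 % | 30 % | 35 % |
|---|---|---|---|---|---|---|
| ±5 % | 16 → 18 | 35 → 38 | 62 → 64 | 97 → 99 | 139 → 141 | 189 → 191 |
| ±10 % | 4 → 7 | 9 → 12 | 16 → 18 | 25 → 27 | 35 → 38 | 48 → 50 |
| ±15 % | 2 → 5 | 4 → 7 | 7 → 10 | 11 → 14 | 16 → 18 | 21 → 24 |
| ±20 % | 1 → 4 | 3 → 5 | 4 → 7 | 7 → 9 | 9 → 12 | 12 → 15 |

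Every cell rises by two or three people.

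**The case against.** The strongest reply is that the plan used a standard planning approximation and applied it without error. That stands: 16 is right on the plan's own formula, so a reader who infers that Table 3 contains arithmetic mistakes would be wrong.

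A second reply is that the SD of 30 % is a round figure described as conservative, in a table whose columns step by five points. Doubt about the SD outweighs the difference between the two quantiles, and a modestly smaller SD removes the shortfall (step 4). This also stands, and it limits the size of the point. The probabilities in step 3 should not be pressed either: a design sized on expected width lands near 50 %, and even 18 completers reach only 56 %.

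Third, no interval method is specified, and PE is a ratio bounded above at 100 %, so a t interval is itself approximate. That is why the figures here are conditional on that assumption. It does not rescue 1.96, which also needs a known SD.

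A reader might also infer that the 30 % threshold for carrying products forward is compromised. The documents do not support this: sections 13.1 and 21.1.3 apply the threshold to the PE estimate, without a confidence bound. Nor is it a contradiction that the 23 per group in section 19.2 fits a t-based power calculation (89.97 % power with 22, 91.2 % with 23, assuming two-sided 5 %). That is a two-group comparison, and nothing requires the same approximation in both sections.

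**Conclusion.** The point holds as a minor correction to a stated precision figure. At an observed SD of 30 %, the half-width exceeds ±15 % by 1.0 percentage point with 16 completers and by 0.4 with 17. In expectation, at a true SD of 30 %, the excess is 0.7 and 0.2 points. The shortfall against the stated margin is two completers (18 rather than 16). These figures rest on a two-sided 95 % level inferred from Table 3 and on a t interval, which the documents neither name nor exclude. The design, the conduct and the selection of products are unaffected.

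**What to change.** Keep 17 participants. In section 19.1, restate the precision as *about ±16 % with 16 completers (±15.4 % with 17) at an SD of 30 %*, and name the confidence level and interval method. Recompute Table 3 with the t distribution; the SD 30 % column becomes 141, 38, 18 and 12 for ±5, ±10, ±15 and ±20 %. This also replaces the cell of one person and gives a sounder table if stage two is resized. The cost is one sentence and one table. The downside is that the stated precision becomes slightly less favourable.
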